8.1.2 DEFINITION OF SERIOUS ADVERSE EVENTS (SAE)

An SAE is any AE occurring at any dose that results in any of the following outcomes (note that if either the investigator or the Sponsor believes that the event is serious, the event must be considered serious and evaluated for expedited reporting). Note that the terms "severe" and "serious" are not synonymous. Severity (or intensity) refers to the grade of an AE. "Serious" is a regulatory definition. A serious adverse event (experience) or reaction is an untoward medical occurrence that, at any dose, fulfills one or more of the following criteria:

- a. Results in death (i.e., the AE actually causes or leads to death)
- b. Is life-threatening
 - An AE is considered "life-threatening" if, in the view of either the investigator or Sponsor, its occurrence places the patient or subject at immediate risk of death; it does not include AEs which, had it occurred in a more severe form, might have caused death
- c. Results in inpatient hospitalization or prolongation of existing hospitalization.
 - Hospitalization for elective treatment of a pre-existing condition that did not worsen during the study is not considered an AE

- Complications that occur during hospitalization are AEs; if a complication prolongs hospitalization, the event is an SAE
 - “Inpatient” hospitalization means the subject has been formally admitted to a hospital for medical reasons that may or may not be overnight; it does not include presentation at a casualty or emergency room unless the event meets the definition of an Important Medical Event (in the opinion of the Investigator or Sponsor)
- d. Results in persistent or significant incapacity or substantial disruption of the ability to conduct normal life functions
- The term ‘disability’ means a substantial disruption of a person’s ability to conduct normal life functions; this definition is not intended to include experiences of relatively minor medical significance such as uncomplicated headache, nausea, vomiting, diarrhea, influenza, accidental trauma (i.e., sprained ankle) that may interfere or prevent everyday life functions but do not constitute a substantial disruption
- e. Results in a congenital anomaly in the offspring of a subject who received drug
- f. Results in an Important Medical Event. Important Medical Events are events that may not result in death, be life-threatening, or require hospitalization but may be considered an SAE when, based upon appropriate medical judgment, they may jeopardize the subject and may require medical or surgical intervention to prevent one of the outcomes listed in this definition; examples of such medical events include allergic bronchospasm requiring intensive treatment in an emergency room or at home, blood dyscrasias or convulsions that do not result in inpatient hospitalization, or the development of drug dependency or drug abuse
- Medical and scientific judgment should be used in deciding whether prompt reporting is appropriate in this situation

8.2 CLASSIFICATION OF AN ADVERSE EVENT

8.2.1 SEVERITY OF EVENT

Each AE or suspected adverse reaction must be assessed for its seriousness and severity. Severity will be assessed by the investigator or designee using the following definitions:

SEVERITY	DEFINITION
MILD	Aware of sign or symptom, but easily tolerated
MODERATE	Discomfort enough to cause interference with usual activity
SEVERE	Incapacitating with inability to work or do usual activity

Outcome will be assessed using the following categories: recovered/resolved, not recovered/ not resolved, recovered/resolved with sequelae, fatal, or unknown.

8.2.2 RELATIONSHIP TO STUDY AGENT

Investigators are required to assess the causal relationship (i.e., whether there is reasonable possibility that the study drug caused the event) using the following definitions:

- Unrelated: another cause of the adverse event is more plausible; a temporal sequence cannot be established with the onset of the adverse event and administration of the study agent; or a causal relationship is considered biologically implausible.

- **Possibly Related:** There is a clinically plausible time sequence between onset of the adverse event and administration of the study agent, but the adverse event could also be attributed to concurrent or underlying disease, or the use of other drugs or procedures. Possibly related should be used when the study agent is one or several biologically plausible adverse event causes.
- **Definitely Related:** The adverse event is clearly related to use of the study agent.

If either the investigator or the Sponsor considers the event related, then the event will be considered related for reporting purposes.

8.2.3 EXPECTEDNESS

The Sponsor or designee will be responsible for determining whether an AE is expected or unexpected. An AE will be considered unexpected if the nature, severity, or frequency of the event is not consistent with the Reference Safety Information described in the Investigator's Brochure.

For example, under this definition, hepatic necrosis would be unexpected (by virtue of greater severity) if the investigator brochure referred only to elevated hepatic enzymes or hepatitis. Similarly, cerebral thromboembolism and cerebral vasculitis would be unexpected (by virtue of greater specificity) if the Investigator's Brochure listed only cerebral vascular accidents. "Unexpected" as used in this definition, also refers to AEs or suspected adverse reactions that are mentioned in the Investigator's Brochure as occurring with a class of drugs or as anticipated from the pharmacological properties of the drug but are not specifically mentioned as occurring with the particular drug under investigation. For example, although angioedema is anticipated to occur in some patients exposed to drugs in the angiotensin-converting enzyme (ACE) inhibitor class and angioedema would be described in the Investigator's Brochure as a class effect, the first case of angioedema observed with the drug under investigation should be considered unexpected for reporting purposes ([FDA 2012](#)).

This definition of "unexpected" relies entirely on the Reference Safety Information in the Investigator's Brochure as the basis for determining if newly acquired information generated from clinical trials or reported from other sources is unexpected. The suspected adverse reactions listed in the Investigator's Brochure (i.e., "expected") are those observed with the investigational drug and for which a causal relationship between the event and the drug is suspected or confirmed.

Sponsor assessment of expectedness and relationship to study drug/causality will determine the need for expedited reporting of AEs.

8.3 TIME PERIOD AND FREQUENCY FOR EVENT ASSESSMENT AND FOLLOW-UP

At every clinic visit, subjects will be assessed for AEs and SAEs. After the subject has had an opportunity to spontaneously mention any problems, the investigator should inquire about AEs by asking a non-leading question such as the following:

1. "How are you feeling?"
2. "Have you had any changes since your last assessment/visit?"
3. "Have you taken any new medicines since your last assessment/visit?"

8.3.1 POST-STUDY AEs AND SAEs

The investigator is not obligated to actively seek SAE information in former study participants, but the investigator is encouraged to notify Alkahest, Inc. or their designee of any AE or SAE occurring within 30 days after a subject completes the study (or has their last visit) that the investigator judges may be reasonably related to study treatment or study participation.

8.4 REPORTING PROCEDURES

8.4.1 ADVERSE EVENT REPORTING

All subjects who have given informed consent will be evaluated for AEs. All AEs that occur after the time of treatment with the study agent will be considered Treatment Emergent AEs. Subjects with Treatment-Emergent AEs must be followed until the AE is resolved or is stable, unless the subject is lost to follow up.

Each AE or suspected adverse reaction must be described as follows: the date of onset, date of resolution, severity (mild, moderate, severe), frequency of the event (single episode, intermittent, continuous), action taken with study treatment (no action taken, treatment held, treatment discontinued), outcome, causality* (unrelated, possibly related, definitely related), and seriousness criteria. Each AE or suspected adverse reaction must be recorded separately.

***Note:** Causality assessment will be made only when the AE occurs after the subject has initiated at least one infusion of the study agent. An AE occurring before the subject’s exposure to study agent will always be labeled as “unrelated”.

Any AE occurring during the study must be documented in the subject’s medical records and as an AE in the CRF. Any SAE occurring during the study must be documented in the subject’s medical records and as an SAE in the CRF.

A separate set of SAE pages should be used for each SAE. However, if at the time of initial reporting, multiple SAEs are present that are temporally and/or clinically related, they may be reported on the same SAE page.

The investigator should attempt to establish a diagnosis of the event (that meets the definition of an AE or SAE) based on signs, symptoms, and/or other clinical information. In such cases, the diagnosis should be documented as the AE and/or SAE and not the individual signs or symptoms. The diagnosis will become the basis for the verbatim term as reported by the investigator. If no diagnosis is known and clinical signs and symptoms are not present, the abnormal finding should be recorded.

In addition to the investigator’s own description of the AE, each AE will be encoded according to the MedDRA.

The investigator will take all appropriate and necessary therapeutic measures required for resolution of the AE. Any medication necessary for the treatment of an AE must be recorded on the concomitant medication CRF.

The SAE pages of the CRF should be completed as thoroughly as possible and signed by the investigator or his/her designee before transmittal to the study Contract Research Organization (CRO). It is very important that the investigator provide his/her assessment of causality to study drug as well as an applicable diagnosis at the time of the initial SAE report.

8.4.2 SERIOUS ADVERSE EVENT REPORTING

8.4.2.1 Timeframes for Reporting SAEs

Under 21 CFR 312.32(c), the Sponsor is required to notify FDA and all participating investigators in a safety report of potentially serious risks from clinical trials [i.e., Suspected Unexpected Serious Adverse Reactions (SUSARS)], as soon as possible after the Sponsor receives the safety information and determines that the information qualifies for reporting:

- No later than 7 calendar days for events that are life threatening (in the opinion of the investigator or the Sponsor) or that involve Death as an outcome.
- No later than 15 calendar days for all other SUSARS.

As such, prompt notification of the Sponsor, and/or the Sponsor's representatives, and promptly providing requested follow-up information regarding SAEs is essential so that ethical and regulatory responsibilities and legal obligations can be satisfied. Investigators are responsible for reporting SAEs according to the following timeframes:

- All SAEs occurring during the study should be reported immediately.
- The SAE Report Form and relevant source documents, if applicable, must be completed and emailed to [contact] within 24 hours of observation or learning of the event.
- Follow-up information must be sent to the CRO within 24 hours of receipt of information by the investigational site.

SAEs will be followed until resolution, the condition stabilizes, the event is otherwise explained or is judged by the investigator to be no longer clinically significant, or until the subject is lost to follow up.

8.4.2.2 SAE Information to Report

All information available regarding an SAE must be submitted in the timeframes indicated. At a minimum, SAE reports must contain the subject ID, the SAE verbatim term, onset date, relationship to study drug/causality, and a brief narrative of the event. Please note that **relationship to study drug/causality as well as the reported verbatim term are very important** and should be included in the initial report as it may impact expedited regulatory reporting requirements for the event. The date of SAE discovery by the site staff should be documented in the source documents.

The investigator must record all relevant information regarding an AE/SAE in the applicable sections of the CRF. It is not acceptable for the investigator to send photocopies of the subject's medical records in lieu of completion of the appropriate AE/SAE pages. However, there may be instances when copies of medical records for certain cases are requested by the CRO and/or the Sponsor. If medical records are submitted to the CRO then all subject personal identifiers must be completely and thoroughly redacted prior to submission.

A blank SAE Report Form and instructions for SAE reporting will be provided to the site and will be maintained in the investigator's study file. The SAE Report Form must be completed and emailed to [contact] according to the timeframes specified in [Section 8.4.2.1](#). The SAE Report Form should include copies of relevant source documents, if applicable. Reconciliation of any discrepancy noted during monitoring and amending the CRF is required.

If new information about an SAE is received or corrections to data are needed, the investigator should complete a new SAE Report Form and check the "follow-up" box on the form. This follow-up SAE Report Form should be

submitted within 24 hours of learning of the information, especially if the new information concerns seriousness, relatedness, or the event term of an AE.

Sites acting under their local IRB should submit all applicable events, unanticipated problems, and safety reports to the site's local IRB, if applicable. All safety reporting deviations should also be submitted to their local IRB, if applicable.

8.4.3 ADVERSE EVENTS OF SPECIAL INTEREST

The following will be considered adverse events of special interest (AESI):

- Clinically-significant peripheral edema or pulmonary edema.
- Systolic blood pressure (BP) < 90 or > 160 mm Hg and/or diastolic BP < 60 or > 100 mm Hg, or a change of > 25% from Day 1 (Visit 3) pre-infusion systolic and/or diastolic BP.
- Reduced kidney function (eGFR < 45 mL/min/1.73 m²).
- Suspected transmission of blood-borne infectious agents.

AESI occurring during the study should be reported within 48 hours of observation or learning of the event, unless the event is serious, in which case the event must be reported according to the timeframes specified in [Section 8.4.2.1](#).

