5.1 INCLUSION CRITERIA

In order to be eligible for inclusion, all subjects must meet the following criteria:

- Male or female, aged 60-90 years (inclusive).
- Diagnosis of probable AD based upon the National Institute on Aging-Alzheimer's Association (NIA-AA) Criteria.
- MMSE Score 12-24 inclusive.
- Modified Hachinski Ischemia Scale (MHIS) score of ≤ 4 .
- Have a dedicated, reliable and competent trial partner (e.g., caregiver or family member) who has frequent contact with the subject (defined as approximately 10 hours per week) who is willing to provide support to the subject to ensure compliance with study requirements. The trial partner should understand the nature of the study and be willing to complete the trial partner scales and functional assessments throughout the study.
- The subject (with support of a trial partner) must be able to follow the study protocol, receive the treatment in the established timeframe, and continue during the follow-up interval.
- The subject and trial partner must be sufficiently fluent in English and have visual and auditory acuity sufficient to be capable of reliably completing all study assessments.

- Provided a signed and dated informed consent form (either the subject and/or subject's legal representative as well as the trial partner) in accordance with local regulations/guidelines/IRB/IEC.
- Adequate renal function as defined by estimated glomerular filtration rate (eGFR) ≥ 45 mL/min/1.73 m² using the Modification of Diet in Renal Disease (MDRD) study equation ([MDRD for Adults \(Conventional Units\) | NIDDK, n.d.](#)).
- Systolic ejection fraction of $\geq 55\%$ on trans-thoracic echocardiogram.
- Willing to spend up to 7 nights in an inpatient study unit during both dosing periods.

In order to be eligible for inclusion in the optional CSF biomarker research, all subjects must meet the following criteria:

- Currently enrolled in the ALK6019-201 study.
- Provided a signed and dated informed consent form for CSF collection (either the subject and/or subject's legal representative) in accordance with local regulations/guidelines/IRB/IEC.
- Not yet dosed in the ALK6019-201 study.

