 1. C-SSRS
 2. MMSE
 3. Savonix Full Battery
 4. ADAS-Cog/11
- Complete MRI **(Visit 8 + 4 days Only)**
- In consenting, eligible subjects, perform final lumbar puncture (after final dosing) and obtain CSF samples for optional biomarker research **(Visit 16 or within 5 days following)**

Visit 9 (Day 28 ±7 days) and Visit 17 (Day 112 ±7 days)

- Review AEs and concomitant medications
- Collect the following:
 - Vital signs
 - Blood samples for interim safety labs (Note: Subjects randomized prior to August 30, 2018, will not participate in the additional interim safety labs at Visit 9 and Visit 17.)
 - Samples for proteomics/epigenetics/biobanking (fasting samples preferred)
- Ensure the subject has had an opportunity to eat a meal prior to cognitive and motor testing
- Perform cognitive and motor testing in the following order unless otherwise specified:
 1. Savonix Full Battery
 2. ADAS-Cog/11
 3. Grooved Pegboard

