7.1.1.2.1 Review of Adverse Events	Previously read: AEs will be reviewed, documented, and reported as required at each visit, beginning at baseline. Now reads: AEs will be reviewed, documented, and reported as required at each visit.	Modified to reflect that AEs and concomitant medications may need to be assessed during split screening visits, as applicable.
3 Objectives and Purpose, 7.1.1.1.13 Magnetic Resonance Imaging, 7.2.2.3 Magnetic Resonance Imaging	Amended to reflect Protocol Clarification Memos #1 and #2.	Protocol clarity and standardization.
7.3 Study Schedule	Previously read: Visit windows (when noted) should be benchmarked relative to the baseline visit for a subject, such that subjects complete the entire study by Day 168 (± 7 days). Now reads: Visit windows (when noted) should be benchmarked relative to Visit 3 for a subject, such that subjects complete the entire study by Day 168 (± 7 days).	Protocol clarity; Visit 3 corresponds to Day 1.
7.3.1 Screening, 17 Schedule of Events	Clarified that AEs and concomitant medications should be collected during split visits, as applicable.	Protocol clarity and standardization.
7.3.4. Treatment, 17 Schedule of Events	Added a ± 7 -day window for Visit 85.	To enhance protocol feasibility.
7.3.4. Treatment, 7.3.5 Follow-Up, 17 Schedule of Events	Modified the schedule for collecting STAT safety laboratory samples.	Based on data from 24 subjects dosed, no clinically significant changes in Na, K, Ca, creatinine, or hematocrit have been detected during the dosing period. Therefore, the frequency of pre-infusion i-STAT lab monitoring has been reduced to every other day during each dosing period.
7.3.5 Follow-Up, 17 Schedule of Events	Added interim safety labs (blood creatinine, blood urea nitrogen, and glomerular filtration rate) at Visits 9 and 17.	To more precisely evaluate potential changes in creatinine levels kidney function over time.
8 Assessment of Safety	Amended the Safety Section to clarify reporting	For protocol clarity and standardization.

Location	Description	Purpose
	requirements for SAEs, AESI, and pregnancy.	
8.2.2 Relationship to Study Agent	
Previously read: Final assessment of causality will be made by the Sponsor.
 
Now reads: If either the investigator or the Sponsor considers the event related, then the event will be considered related for reporting purposes.
	Sponsor decided to use a more conservative approach to causality determination.

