6.1.5 Analysis Methods

There will be no formal statistical testing unless indicated otherwise.

A summary will be provided for the following TEAEs per period and overall (Table 14.3.1.1.1-14.3.1.1.3):

- Subjects with Any TEAE
- Subjects with Any Study Drug-Related¹ TEAE
- Subjects with Any TEAE with an Outcome of Death
- Subjects with Any Serious TEAE
- Subjects with Any Study Drug-Related Serious TEAE
- Subjects with Any TEAE Leading to Discontinuation of Study Drug
- Subjects with Any Study Drug-Related TEAE Leading to Discontinuation of Study Drug
- Subjects with Any TEAE of Special Interest
- Subjects with Any Study Drug-Related TEAE of Special Interest

The adverse events will be shown by MedDRA system organ class and preferred term, in order of descending overall frequency. For each AE, the percentage of subjects who experience at least 1 occurrence of the given event will be summarized per period and overall. Incidence tabulations will be provided for overall summary (Table 14.3.1.2.1-14.3.1.2.3), summary by highest severity (Table 14.3.1.3.1-14.3.1.3.3), and summary by relatedness (Table 14.3.1.4.1-14.3.1.4.3).

Incidence of Serious TEAEs, TEAEs of Special Interest, TEAEs Leading to Subject Withdrawal and TEAEs Leading to Death will be tabulated by MedDRA System Organ Class and Preferred Term (Table 14.3.1.5.1-14.3.1.5.4), and listed as well (Listing 14.3.1.6.1-14.3.1.6.4).

Adverse events with preferred terms associated with blood pressure changes will also be presented by infusion period, SOC, PT, and treatment group. Infusion

period will be further categorized by whether the event start date occurred during the infusion period or after the infusion period. Examples of such events can be identified by the following preferred terms: blood pressure decreased, blood pressure diastolic decreased, blood pressure systolic decreased, blood pressure increased, increased blood pressure, blood pressure diastolic increased, blood pressure systolic increased, hypotension, hypertension, low blood pressure, high blood pressure. This is a non-exhaustive list and a review of AE MedDRA coding will be conducted prior to lock to identify all events associated with blood pressure changes. (Table 14.3.1.7.1-14.3.1.7.3).

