6.2 Clinical Laboratory Evaluations

Numeric measurements of hematology, serum chemistry, urinalysis and urine chemistry will be investigated. Changes from baseline for all safety lab parameters will be summarized at each scheduled timepoint (Table 14.3.2.1.1-14.3.2.1.3). Frequency tables for categorical test results will be tabulated at each scheduled timepoint (Table 14.3.2.2). Shift tables from the baseline to each post-baseline scheduled timepoint will be presented (Table 14.3.2.3.1-14.3.2.3.3).

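### The renal AESI has the entry limit of eGFR 45 as its only trigger, and SAP 6.2 has no subject-level count below 45 and no worst percent decline to offset this

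*Protocol*

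**What the plan says.** Entry (Protocol 5.1) requires "Adequate renal function as defined by estimated glomerular filtration rate (eGFR) ≥ 45 mL/min/1.73 m²" by the MDRD equation. The renal AESI (Protocol 8.4.3) is "Reduced kidney function (eGFR < 45 mL/min/1.73 m²". The blood-pressure AESI in the same list has absolute limits and also a relative limb: "or a change of > 25% from Day 1 (Visit 3) pre-infusion systolic and/or diastolic BP". The renal item has no such limb.

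The revision history (Protocol 18) shows that the renal item came in with Version 5.0, dated 30 August 2018. The AESI list before that covered fluid-related events and blood-borne infection. The same revision justifies a laboratory change with "Based on data from 24 subjects dosed", and it adds creatinine, BUN and eGFR at Visits 9 and 17 to follow kidney function. Protocol 7.3.5 limits who gets them: "Subjects randomized prior to August 30, 2018, will not participate in the additional interim safety labs at Visit 9 and Visit 17".

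On analysis, SAP 6.1.5 states: "Incidence of Serious TEAEs, TEAEs of Special Interest, TEAEs Leading to Subject Withdrawal and TEAEs Leading to Death will be tabulated". The AESI table is thus built from reported events. SAP 6.2 summarises change from baseline at each scheduled timepoint and adds: "Shift tables from the baseline to each post-baseline scheduled timepoint will be presented". Protocol 10.4.4 describes such shifts as numbers of subjects relative to the reference range. SAP 2.6 requires the minimum and maximum as well as the mean, median and SD.

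For blood pressure, SAP 6.3 counts subjects from the measurements themselves, including a change above 30%. SAP 8 gives the reason: which blood-pressure values became AESIs was left to the investigator. There is no renal counterpart.

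**The concern.** Because the AESI limit and the entry limit coincide, the AESI responds to where a subject started as well as to how far kidney function fell. A subject admitted at 46 can be flagged by ordinary variation, while one who goes from 90 to 46 is not flagged. A laboratory value also becomes an adverse event only if judged clinically significant (Protocol 7.2.1 and 8.1.1), so the count carries the investigator dependence that led the SAP to add measurement-based counts for blood pressure.

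Enrolment date matters too. Subjects dosed before Version 5.0 spent part or all of their follow-up without a renal AESI category, and those randomised before 30 August 2018 have two fewer scheduled eGFR values. The documents do not say whether earlier data were re-read against the new item.

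Safety is a primary endpoint, in about 40 subjects, where a few individuals carry the information. A summary per subject is what shows an individual decline.

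**Working it through.** No figure in the plan bears on this point, so there is none to reproduce first.

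**1. Fall needed to become an AESI.** Formula: 1 − 45/baseline, with 45 from Protocol 8.4.3.

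| Baseline eGFR | Fall must exceed |
|---|---|
| 46 | 1 − 45/46 = 2.2% |
| 50 | 1 − 45/50 = 10% |
| 60 | 1 − 45/60 = 25% |
| 75 | 1 − 45/75 = 40% |
| 90 | 1 − 45/90 = 50% |

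Conversely, a 25% fall is not flagged from a baseline of 60 or more (45/0.75), and a 30% fall is not flagged from about 64.3 or more (45/0.70).

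**2. Scheduled post-dose central-lab eGFR values** (Protocol 7.3 and 17). Comprehensive labs at Visits 4, 6, 8, 10, 12, 14, 16 and 18, plus the exit panel at Visit 19, give 9. Visits 9 and 17 make 11 for later subjects. Visits 3 and 11 have only i-STAT chemistry, whose panel does not list eGFR. The scheduled central-lab baseline is therefore the screening value, the one that decided eligibility.

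**3. Chance crossing with no true change.** P(at least one of k values < 45) = 1 − [1 − Φ((45 − b)/(CV × b))]^k, where b is the true eGFR. The CV is not in the documents; 5, 8 and 10% are assumed, with independent errors. Example for b = 50, CV 5%, k = 9: z = −5/2.5 = −2, Φ = 0.0228, and 1 − 0.9772^9 = 0.187.

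| True eGFR | 9 values, CV 5 / 8 / 10% | 11 values, CV 5 / 8 / 10% |
|---|---|---|
| 46 | 97 / 99 / 99% | 99 / 100 / 100% |
| 50 | 19 / 63 / 79% | 22 / 71 / 85% |
| 55 | 0.1 / 10 / 27% | 0.2 / 12 / 32% |
| 60 | 0 / 0.8 / 5.5% | 0 / 1 / 7% |

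These are chances of a laboratory crossing, not AESI rates, since reporting also needs clinical judgement.

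**4. How well the limit tracks decline.** Simulation under assumptions: subjects screened at a measured value of 45 or more, 10% with a sustained 30% fall, 11 values, CV 5 to 8%, any value below 45 counted.

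| Assumed baseline mean (SD) | True fallers caught | Flagged subjects who truly fell |
|---|---|---|
| 65 (12) | 63–75% | 48–62% |
| 75 (15) | 35–45% | 57–68% |
| 85 (15) | 15–23% | 71–80% |

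**5. A relative limit for comparison, illustration only.** With no true change, 11 values and one baseline value, a fall above 25% appears by chance in 0.04 / 5.4 / 16.7% of subjects at CV 5 / 8 / 10%. A fall above 30% appears in 0.0 / 1.1 / 6.1%. In this model neither depends on the baseline level.

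**The case against.** The case against is substantial.

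- A reader might infer that the SAP has no laboratory-based renal count. It has one: the shift tables count subjects. The change tables also carry minima, so a scheduled fall from 90 to 46 would show as a change of −44 or lower in that visit's minimum. Listing 16.2.8.1 holds the laboratory results. What remains is narrower. The shifts use a reference range, not 45. By-visit minima do not show how many subjects fell, by what percentage, or whether two visits show the same person. SAP 2.3 keeps unscheduled values out of per-timepoint summaries and allows them for worst-case determination, but SAP 6.2 specifies no worst-case table.
- A reader might infer that the AESI merely marks who started near 45. The simulation does not support that: about half or more of flagged subjects (48–80%) truly fell. In addition, a clinically significant fall that stays at or above 45 is still recorded as an ordinary adverse event (Protocol 7.2.1).
- A reader might infer that the doses cannot be compared on renal decline. Randomisation is concurrent, in blocks of 2 and 4 within sex (SAP 1.4), so in expectation both doses share the baseline mix, the change of definition and the missing visits. The loss is in sensitivity and interpretability.
- A reader might take 40 − 24 = 16 as a ceiling on subjects with Visit 9 and 17 renal labs. Enrolment is approximate and replacement is allowed (Protocol 5.4.2 and 10.5), so it is not a firm bound.
- Baseline eGFR is not documented, so the number of subjects near 45 is unknown, and samples taken days apart are unlikely to have fully independent errors. Both points stand and limit the size of the claim.

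**Conclusion.** The concern holds for the table of reported renal AESIs. Its trigger equals the entry limit and has no relative limb: a fall of just over 2% suffices from 46, while even a 50% fall from 90 is not flagged. Its ascertainment changed part-way through enrolment. The SAP has no subject-level count below 45 and no worst percent decline, although it has measurement-based counts for blood pressure.

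The threshold arithmetic, the timing and the contents of the SAP come from the documents. The chance-crossing and detection figures rest on an assumed CV, independent errors and assumed baseline distributions, and should be read as ranges. Near 45 the chance of a crossing is high; by 60 it is small.

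The renal data are not lost: they are summarised by visit and listed. This is a worthwhile, low-cost improvement to a primary safety analysis.

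**What to change.** Leave the AESI definition and its reporting as they are. Before database lock, add one table to SAP 6.2, by dose, for all Safety Set subjects regardless of protocol version, from central-lab eGFR including post-dose unscheduled values. It should give, overall and by dosing course:

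- worst post-dose eGFR per subject;
- worst percent change per subject from the baseline before the first dose (SAP 2.3);
- n (%) below the protocol's own limit of 45;
- each of these split by baseline eGFR.

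Use the pre-first-dose baseline for both courses. Resetting it at the second course could hide a cumulative loss: 90 to 69 is 21/90 = 23%, 69 to 53 is 16/69 = 23%, but 90 to 53 is 37/90 = 41%.

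Base the main table on the nine visits common to all subjects plus unscheduled values, and show Visits 9 and 17 separately. The baseline split and any relative-decline cut-off are for the sponsor to pre-specify while blinded.

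The cost is the programming of one table from data already collected. The downside is that the worst of many values will include some chance crossings near 45; the baseline split and the percent-change column let the reader see this.
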